9.2.6 Adverse Events of Special Interest

ONO-7475

Adverse events of special interest have yet to be defined for ONO-7475.

Venetoclax

Adverse events of special interest for venetoclax when taken in combination with ONO-7475 have yet to be defined.

9.2.7 Events Not To Be Reported as Serious Adverse Events

The following events do not qualify as SAEs as defined in Section 9.2.1.

Any planned hospitalizations or hospitalizations purely for diagnostic purposes (as required by the protocol) do not qualify as AEs or SAEs and do not require reporting.

A brief stay in an outpatient clinic or emergency room which does not involve formal admission or overnight stay does not qualify as a SAE and does not require reporting (medical judgement should be applied to assess if the reported event term would nevertheless qualify as medically important event as per Section 9.2.1).

Admission to a nursing home due to purely social reasons and in the absence of deterioration in the patient's general health status is captured in the source data but does not qualify as AE or SAE and does not require immediate reporting.

9.3 Progression of Underlying Malignancy

Progression or relapse of the malignancy will not be reported as an SAE, however unexpected clinical signs or symptoms that do not fit the expected pattern of AML or MDS disease progression must be reported, even if they are eventually attributable to disease progression or relapse.

If there is any uncertainty on the part of the Investigator and/or Sponsor about an AE being attributable only to the disease under study, it should be reported as an AE or SAE.

[REDACTED]

10 DATA ANALYSIS AND STATISTICAL CONSIDERATIONS

10.1 Study Design Considerations

10.1.1 Sample Size Assumptions and Design Considerations

Part A

[REDACTED]

[figure not shown]
Approximately 42 patients across approximately [REDACTED] cohorts will be enrolled for dose escalation in Part A. This is based on the assumption that it may take up to [REDACTED] cohorts ([REDACTED]) to determine an efficacious dose of ONO-7475 monotherapy in R/R AML or R/R MDS.

Part D

[REDACTED] DLT evaluable (for definition of evaliability see Section 3.3.2) are required for the SA analysis [REDACTED]

[REDACTED] Analysis of the safety, tolerability, PK and PD data will occur once there are [REDACTED] DLT evaluable patients.

The EA of the study has 2 stages following Simon's 2-stage design. The null hypothesis is that the CR/CRh rate associated with the combination therapy is $\leq 20\%$ versus the alternative hypothesis that the CR/CRh rate is $\geq 40\%$. Under the minimax design criterion, a total sample size of 41 is required to test the above hypotheses with a 1-sided significance level of 0.023 and 80.26% power. The number of EA evaluable patients will include SA group patients who met EA evaluable criterion (i.e., patients who had at least 1 dose of ONO-7475 and/or venetoclax at the same planned dose level, 6 mg or 10 mg).

10.2 Data Analysis Considerations

10.2.1 Analysis Populations

The SAF will be based on all patients who have been enrolled into the study and who have received at least 1 dose of ONO-7475 for Part A or who have received at least 1 dose of venetoclax and/or ONO-7475 for Part D. The patients in the SAF will be grouped by the initial dose level of ONO-7475 actually received. The SAF will be used for all safety analyses by default.

Since it is feasible patients may receive study drug at different dose levels for varied lengths of time, 2 alternative groupings are defined for the SAF: one is by the highest dose received and the other is by dose received for the longest duration (in the case that 2 or more dose levels are administered for the same duration, the highest dose level will be selected). These will be used only for supportive safety analyses.

The Full Analysis Set (FAS) will be the primary analysis set used for assessment of efficacy and will be based on all patients who have been enrolled into the study and who have received at least 1 dose of ONO-7475 for Part A or who have received at least 1 dose of venetoclax and/or ONO-7475 for Part D. The patients in the FAS will be grouped by the dose level as assigned at the study entry. The FAS will be used for all demographic and baseline summaries and all efficacy

Study Number: ONO-7475-01 Protocol	Version: 10.0 [incorporating Amendments #1–9]
--	--

analyses. For Part A, the efficacy summaries will focus on the subset of the FAS who are diagnosed with AML. For Part D, patients in the FAS may be replaced if the efficacy analysis is compromised by extenuating circumstances (for example, a pandemic in which patient site visits are not possible and therefore clinical response cannot be evaluated).

The Response Evaluable Analysis Set for Part D will be based on all patients who received at least 1 dose of venetoclax and/or ONO-7475 and whose response has been determined by the **Revised Recommendations of the IWG for Response Criteria, in Acute Myeloid Leukemia** (Section 13.8). Patients in the Response Evaluable Analysis Set will be grouped by the dose level as assigned at the study entry.

The PK Analysis Set will include patients who are administered ONO-7475 for Part A or ONO-7475 or venetoclax for Part D, and from whom results of plasma concentrations are obtained for at least 1 sampling point. Patients in the PK analysis set will be grouped based on the dose level received during the PK sample collection period. If necessary, there will be 2 PK Analysis Sets in Part D; 1 for ONO-7475 and 1 for venetoclax.

The PD Analysis Set will include patients who have received at least 1 dose of ONO-7475 for Part A or ONO-7475 or venetoclax for Part D, and from whom results of PD collection assays are obtained for at least 1 sampling point which is suitable for analysis. Patients in the PD analysis set will be grouped based on the initial dose they actually received.

Detailed definitions of the analysis sets will be provided in the Statistical Analysis Plan (SAP).

10.2.2 Key Elements of Analysis Plan

All data will be presented in the most appropriate manner allowing for type and distribution.

Where appropriate, summaries will be made for each dose level.

Details of summaries and analyses of the data, including where patients may have changed their ONO-7475 dose level, will be provided in the SAP.

Continuous variables will be summarized using mean, standard deviation, median, minimum and maximum, and categorical variables will be summarized using frequencies and percentages.

Baseline and demographic characteristics (e.g., age, sex etc.) will be summarized as continuous or categorical variables, as appropriate.

Statistical analysis, including the PK analysis for after database lock, will be described in the SAP.

10.2.2.1 Efficacy analyses

The CR/CRh rate in Part D is defined as the proportion of patients who have a best overall response in AML or CRh.

ORR is defined as the proportion of patients who achieve responder status, i.e., having a best overall response in AML and MDS including:

[AML]

- CR
- CRh (Part D only)
- CRI (note for Part D this will constitute CRI patients who did not meet the requirements for CRh)
- Morphologic leukemia-free state
- PR

[MDS]

- CR
- Marrow CR
- PR

Patients who do not have sufficient baseline or on-study efficacy status information to be adequately assessed for response status (i.e., those with best overall response of not evaluable) or received anti-leukemic therapy other than the study treatment prior to becoming a responder (per the definition above) will be considered as non-responders. Patients with a best overall response of treatment failure (Parts A and D patients with AML), failure or stable disease (Part A patients with MDS), progression (per the definition given below), or missing response assessments, will be considered non-responders.

Best Overall Response is defined as the best response assessment assigned to a patient at any time-point during the study up to and including progression, prior to the patient's study completion and prior to initiation of any other anti-leukemic therapy.

Time to Response (TTR) is defined as the duration in months from the date of first study treatment to the date of first documentation of responder status (per definition above). TTR is not defined for patients who do not achieve a best overall response of PR or better.

DoR is defined as duration in months from the date of first documentation of responder status (per definition above) to the date of disease progression or death due to any cause, whichever is earlier. DoR is not defined for patients who do not achieve a best overall response of PR or better.

Study Number: ONO-7475-01 Protocol	Version: 10.0 [incorporating Amendments #1-9]
--	--

If the specified event does not occur, the DoR will be censored at the date of last adequate efficacy assessment. If there is no adequate assessment available after the first documentation of responder status (per definition above), the DoR will be censored at the date when responder status is first recorded.

The date of definitive progression will be the time point at which progression is first identified. Progression is defined as disease recurrence for AML in Parts A and D, relapse after CR or PR and disease progression in MDS (per IWG criteria for MDS).

An adequate tumor assessment is defined as one with an outcome other than “Not Evaluable”.

EFS is defined as the duration in months from the date of first study treatment to treatment failure (for AML patients in Parts A and D), failure (for MDS patients in Part A), progression (per definition above), or patient death from any cause.

If the specified event does not occur, the EFS will be censored at the date of last adequate efficacy assessment. If there is no adequate assessment available, the EFS will be censored at the date of first study treatment.

OS is defined as duration in months from the date of first study treatment to death from any cause. OS will be censored at the date last known to be alive for patients who are still alive.

The primary efficacy variables will be listed and summarized using descriptive statistics based on the FAS for each part of the study.

The CR/CRh rate (for Part D only) and ORR will be calculated using the FAS. The 2-sided 95% exact confidence intervals of the CR/CRh rate and ORR will be estimated using the Clopper-Pearson method.

The rate of CR/CRh without MRD will be provided for patients in Part D.

The rates of CR and CRh will also be provided separately for patients in Part D.

TTR will be summarized descriptively as a continuous variable for those patients who achieve PR or better.

[figure not shown]
DoR will be characterized using the Kaplan-Meier method for patients who achieve PR or better (in Part A) and CR/CRh (in Part D). Medians, 25th percentile (Q1), 75th percentile (Q3), minimum and maximum will be provided along with the 95% confidence intervals for the median. Kaplan-Meier curves will be provided.

OS and EFS will be analyzed for all patients in a similar manner to DoR.

For Part A, the efficacy endpoint summaries will focus on AML patients only.

In addition, the CR/CR_h rate analysis will be repeated using the Response Evaluable Analysis Set as a supportive analysis for Part D and the ORR analysis will be repeated using the Response Evaluable Analysis Set as a supportive analysis for Part D.

If necessary (for example in the case of a pandemic disease whereby there is an inordinate amount of missing data), the amount of missing efficacy data may be reviewed and appropriate multiple imputation methods may be applied for analytical purposes.

Full details of all planned analyses will be provided in the SAP.

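### Part D duration of response is analysed only in CR/CRh patients, yet its clock can start at an earlier PR, MLFS or CRi, so it overstates how long CR/CRh lasts

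*Combined protocol and SAP*

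**What the plan says.** All of the relevant text is in protocol Section 10.2.2.1.

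- **Start of the clock.** "DoR is defined as duration in months from the date of first documentation of responder status (per definition above").
- **What responder status means.** "ORR is defined as the proportion of patients who achieve responder status, i.e., having a best overall response in AML and MDS including" a list that for AML in Part D holds CR, CRh, CRi, "Morphologic leukemia-free state" and PR.
- **Event.** The interval runs "to the date of disease progression or death due to any cause, whichever is earlier".
- **Who has a DoR.** "DoR is not defined for patients who do not achieve a best overall response of PR or better".
- **Who is analysed.** "DoR will be characterized using the Kaplan-Meier method for patients who achieve PR or better (in Part A) and CR/CRh (in Part D").
- **Best response.** "Best Overall Response is defined as the best response assessment assigned to a patient at any time-point during the study up to and including progression".

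Time to response ends on the same date on which DoR begins. DoR is a secondary endpoint of the Part D expansion efficacy group (Section 2, Table 4), whose primary endpoint is the CR/CRh rate. Section 13.8 (Appendix 8) reproduces the AML response criteria, and these measure remission duration from the date of CR.

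**The concern.** In Part A the clock and the analysed group broadly match: both rest on PR or better. In Part D the group was narrowed to CR/CRh but the clock was left at the first response of any listed kind. Membership of the analysis then depends on a later event (CR/CRh) while time is counted from an earlier one (first PR, MLFS or CRi). That is immortal time.

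The resulting curve is not the duration of CR/CRh, because it starts too early for some patients. It is not the duration of overall response either, because responders who never get beyond PR, MLFS or CRi are left out. Restricting the analysis to the categories of the primary endpoint invites readers to take the median as how long CR/CRh lasts, and in that reading it is too long. The more often responses deepen stepwise, the larger the excess.

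**Working it through.** **1. Following one patient through the rules.** Suppose PR is documented at the end of cycle 1 and CR at the end of cycle 3.

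- Responder status is first documented at the end of cycle 1, so DoR starts there.
- Best overall response is CR, so the patient is in the Part D analysis.
- Had the patient progressed or died between those dates, best overall response would have stayed at PR, because it is taken only up to progression. The patient would then be out of the analysis.

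So no event can occur between first lesser response and CR/CRh among the patients analysed. For each of them:

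DoR as written = (time from CR/CRh to event) + (lag from first response to CR/CRh), with lag ≥ 0.

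The direction is fixed: zero for patients whose first documented response is CR or CRh, upward for the rest, never downward.

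**2. How many patients.** The plan states no figure for DoR. Its nearest figure is the Simon minimax design in Section 10.1.1 (20% versus 40%, N = 41, one-sided 0.023, power 80.26%). An exact binomial search with one-sided alpha at most 0.025 and power at least 80% reproduces it: stop if at most 5 of 22 respond, otherwise declare success with more than 13 of 41; alpha 0.0225, power 0.8026. At a 40% rate the DoR analysis would hold about 0.40 × 41 ≈ 16 patients; a positive trial needs at least 14.

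**3. Size of the shift.** The documents give neither the CR/CRh duration, nor the share of patients with a lag, nor the lag; the assessment schedule is blacked out. Assume:

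- true CR/CRh duration exponential with median m = 4 or 6 months, so λ = ln 2 / m;
- a share f = 25%, 50% or 75% of CR/CRh patients first documented at a lesser response;
- a fixed lag L of one or two 28-day cycles, 28/30.44 = 0.92 or 56/30.44 = 1.84 months.

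For t > L, the survival function as written is S(t) = e^(−λt) × (1 − f + f·e^(λL)). Setting it to one half gives

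median as written = m + ln(1 − f + f·e^(λL)) / λ, roughly m + f × L.

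Example: m = 4, f = 0.75, L = 1.84. Then λ = 0.1733, e^(λL) = 1.376, the bracket is 0.25 + 0.75 × 1.376 = 1.282, and ln(1.282)/0.1733 = 1.43. The median is 5.43 months. The 6-month rate is 0.354 × 1.282 = 45.3%.

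| Share f | Lag | Median, true 4 mo | Six-month rate (true 35.4%) | Median, true 6 mo |
|---|---|---|---|---|
| 25% | 28 d | 4.24 | 36.9% | 6.24 |
| 25% | 56 d | 4.52 | 38.7% | 6.50 |
| 50% | 28 d | 4.48 | 38.4% | 6.47 |
| 50% | 56 d | 4.99 | 42.0% | 6.97 |
| 75% | 28 d | 4.70 | 39.9% | 6.70 |
| 75% | 56 d | 5.43 | 45.3% | 7.42 |

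The shift is +0.2 to +1.4 months for either true median. Simulation of the 4-month case agrees to within simulation error. If every CR/CRh patient had the same lag, the median would rise by exactly that lag; a lag of 3 months in all patients, an extreme case, would turn 6 months into 9.

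**4. With the clock at first CR or CRh.** The lag term disappears and the Kaplan-Meier median estimates the CR/CRh duration itself.

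**The case against.** The protocol defers full analysis detail to the SAP (Sections 10.2.2 and 10.2.2.1), and Section 10.2.4 allows Part D updates before database lock, so a Part D start date could still be set there. That is where the repair can be made, but nothing in the supplied text changes the origin.

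The sentence naming the Part D group could also be read as setting the qualifying response for that part, with the clock following it. That reading is possible but less natural: the definition refers explicitly back to responder status, and a rule that can be read two ways needs settling anyway.

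It is fair to say that the protocol names no endpoint called duration of CR/CRh, and that the quantity matches its literal definition as time from any first response. It misleads only when read as CR/CRh duration, which the restriction to CR/CRh invites.

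The limits on consequence also stand. Patients who go straight to CR or CRh contribute no lag, so the excess could be near zero. Every input to the size is assumed. DoR is descriptive and carries no test. With 16 events and an exponential model, the 95% interval around a median of 4 months is about 2.6 to 7.0 months, so the shift lies within sampling error. But sampling error does not cancel a shift that can go only one way.

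**Conclusion.** The concern holds. As written, Part D DoR pairs a start date from one set of responses with a population from a narrower set, and the time between the two is guaranteed event-free. The mismatch and its direction follow from the text alone. Its size does not: +0.2 to +1.4 months on a median of 4 or 6 months rests on exponential durations, 25–75% of CR/CRh patients with an earlier lesser response, and a lag of one or two 28-day cycles. The CR/CRh rate, its hypothesis test and the sample size of 41 are untouched. This should be corrected because the result describes the durability of the primary endpoint and the repair is nearly free.

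**What to change.** In Section 10.2.2.1, and in the SAP before Part D database lock, define Part D DoR in CR/CRh patients as the time from first documentation of CR or CRh, whichever comes first, to disease progression (recurrence) or death from any cause. Align the fallback censoring date: a patient with no adequate assessment after first CR or CRh is censored on that date.

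If duration of overall response is also wanted, report it separately from first responder status, in all ORR responders and not only in those who reach CR/CRh. Because time to response ends at first responder status, add time to first CR or CRh so that it joins up with the new DoR.

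The cost is a few sentences. No new assessment should be needed, since the plan already requires dated responses by category. No patient's treatment changes. The reported median may be somewhat shorter.

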10.2.2.2 Pharmacokinetic and Pharmacodynamic Analyses

Plasma concentrations of ONO-7475 and venetoclax (Part D only) will be used to calculate relevant PK parameters. Calculated PK parameters will include: C_{max}, T_{max}, AUC, T_{1/2}. Details will be provided in the SAP.

For assessment of the effect of food on the PK of ONO-7475 C_{max} and AUC [REDACTED] will be calculated in Part A.

The plasma concentration versus time data obtained in this study may be combined with the PD data (PIA assay) obtained. This data will be used to develop a quantitative PK/PD model and support dose selection.

As needed, the concentration versus time data obtained in this study may be combined with PK data from future studies conducted as part of the clinical development program. This data will be used to develop a population PK/PD model using a non-linear mixed-effects modelling approach. This model will be used to evaluate the effects of various covariates on the PK and PD of ONO-7475.

10.2.2.3 Biomarker Analyses

Parameters such as mean, standard deviation, median, minimum and maximum will be calculated for PD (PIA assay) data. The PIA data will be reported in the CSR.

As needed, exploratory data analyses will be conducted for the other biomarker data. These analyses will be detailed in a separate analysis plan and the results reported separately from the CSR.

Study Number: ONO-7475-01 Protocol	Version: 10.0 [incorporating Amendments #1–9]
--	--

10.2.2.4 Safety Analyses

The SAF will be used for all safety analyses by default.

Safety will be evaluated by monitoring all AEs and SAEs.

All AEs will be tabulated and graded according to NCI CTCAE version 4.03 for each patient cohort. Verbatim descriptions of AEs reported during the study period will be mapped to Medical Dictionary for Regulatory Activities (MedDRA) preferred terms and body systems.

Treatment-emergent AEs are defined as:

- Any AEs with an onset date on or after the study drug start date and no later than 30 days after permanent discontinuation of study drug (or initiation of new anti-cancer therapy, whichever occurs first)

All treatment-emergent AEs will be summarized in frequency tables.

For any AE summary showing the AEs by NCI CTCAE grade, the highest grade will be used for those AEs that occurred more than once in an individual patient during the study.

The DLTs will be summarized in frequency tables and also listed.

Laboratory safety assessments will include regular, routine monitoring of hematology and blood chemistry, and urinalysis.

Laboratory data collected during the study will be analyzed and summarized using both quantitative and qualitative methods. Summaries of laboratory data will be provided and will include data collected up to the last dose of study drug plus 30 days for patients who have permanently discontinued study drug.

Laboratory NCI CTCAE grades at baseline and worst post baseline will be summarized in shift tables.

Body weight and vital signs and their change from baseline will be summarized.

Descriptive statistics will be used to summarize ECOG performance status.

A summary of ECG parameters will be provided for each scheduled time point and categorical summaries of maximum observed and change from baseline values will be presented for QTcF.

Prior and concomitant medications will be summarized.

Full details will be provided in the SAP.

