2 STUDY OBJECTIVES AND ENDPOINTS

Table 4 below outlines the primary, secondary, and exploratory objectives of the study and their associated endpoints.

Table 4 Objectives and Endpoints for all study parts

Part A – Monotherapy Dose Escalation	
Primary Objective	Primary Endpoints
To assess the safety and tolerability of ONO-7475 monotherapy in patients with R/R AML or R/R MDS	
• Incidence, nature, and severity of AEs and serious AEs (SAEs)• Clinically significant changes in ophthalmology parameter examinations and 12-lead electrocardiogram (ECG)

Study Number: ONO-7475-01 Protocol	Version: 10.0 [incorporating Amendments #1–9]
--	--

Secondary Objectives	Secondary Endpoints
To select an optimal dose of ONO-7475 for further clinical evaluation	Maximum tolerated dose (MTD) and/or recommended pharmacological dose based on clinical response or pharmacodynamics (PD) markers
To assess the pharmacokinetics (PK) of ONO-7475 in patients with R/R AML and R/R MDS	PK parameters: maximum observed plasma concentration (Cmax), time to reach Cmax (Tmax), area under the plasma concentration-time curves (AUC) on Days 1 and 28, elimination half-life (T1/2) plasma concentration prior to next dose
To evaluate food effect on the PK of ONO-7475	The PK of the food effect on ONO-7475 (Cmax, Tmax, AUC, T1/2, and plasma concentration prior to next dose)
To assess the PD activity of ONO-7475 in patients with R/R AML and R/R MDS	PD biomarkers of response: plasma inhibitory activity (PIA) assay (pAxi/pMer inhibition)
To assess the preliminary clinical efficacy of ONO-7475 in patients with R/R AML and R/R MDS	
 Overall response rate (ORR), duration of response (DoR), event-free survival (EFS) Complete remission (CR) without minimal residual disease (MRD)

Part D – Combination with Venetoclax

Primary Objectives	Primary Endpoints
SA group: To assess the safety and tolerability of ONO-7475 in combination with venetoclax EA group: To assess the preliminary efficacy of ONO-7475 in combination with venetoclax	SA group: Incidence, nature, and severity of AEs and SAEs EA group: CR/CR with partial hematologic recovery (CRh) rate
Secondary Objectives	Secondary Endpoints

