9.1.3 Adverse Event Reporting

The Investigator, or authorized designee, should regularly ask the patients how they are feeling to encourage AE reporting. The person approaching the patients should use a non-leading question such as “How are you feeling?”.

All observed or volunteered AEs, regardless of suspected causal relationship to study drug, will be recorded on the AE page(s) of the eCRF.

In addition, abnormal objective test findings (e.g., ECG changes, abnormal laboratory test results) that result in a change in the study drug dosage or in discontinuation of the drug, or require intervention or diagnostic evaluation to assess the risk to the patient, should be recorded as AEs. Clinically significant changes in physical examination findings and objective test findings should also be recorded as AEs.

Study Number: ONO-7475-01 Protocol	Version: 10.0 [incorporating Amendments #1–9]
--	--

Adverse events will be collected from the time informed consent is given until the patient has completed the study.

Any AEs that are ongoing at the time the patient completes the study will be followed by the Investigator until the AEs are resolved, the patient's condition is stable or persistent, the patient's death, or until the patient is lost to follow-up. Any pregnancies reported after completion of the study must also be reported as per Section 9.2.5.

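### The treatment-emergent AE definition has no worsening clause, so an AE that starts between consent and first dose and rises in grade on treatment is left out of the TEAE frequency tables

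*Combined protocol and SAP*

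**What the plan says.** Section 10.2.2.4 (Safety Analyses) gives one criterion for a TEAE, the onset date. The window opens with "Any AEs with an onset date on or after the study drug start date" and closes with "and no later than 30 days after permanent discontinuation of study drug", or at the start of new anti-cancer therapy if that comes first. Nothing is said about an event already present at first dose that then worsens.

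The same section plans two kinds of AE output:

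- Without a treatment window: "All AEs will be tabulated and graded according to NCI CTCAE version 4.03 for each patient cohort".
- With the treatment window: "All treatment-emergent AEs will be summarized in frequency tables".

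Where AEs are shown by grade, "the highest grade will be used for those AEs that occurred more than once in an individual patient during the study". Laboratory grades at baseline and at their worst afterwards go into shift tables.

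On collection, Section 9.1.3 states: "Adverse events will be collected from the time informed consent is given until the patient has completed the study". Events with a pre-dose onset are therefore in the database by design. Table 4 in Section 2 words the primary safety endpoint of Part A, and of the Part D safety assessment (SA) group, as AEs and SAEs, with no treatment-emergent qualifier.

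**The concern.** A TEAE table is meant to show what happened on treatment. A clinical event that was mild before the first dose and became severe afterwards is an on-treatment finding, because the part that matters occurred after exposure began. Under a rule based only on onset, that event keeps its pre-dose date and is excluded at every grade, including the grade it reached on drug.

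The study population makes this foreseeable. Exclusion criterion 8 in Section 4.3.2 admits patients whose prior-therapy effects have recovered to Grade 1 or have stabilized, and criterion 6 excludes only serious active infection. Patients can therefore start dosing with conditions that have room to worsen.

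Incidence, nature and severity of AEs is a primary endpoint in Part A and the primary endpoint of the Part D SA group. The SA group analysis in Section 10.2.3.1 is made cohort by cohort. The rule can only remove events of this kind; it cannot add any.

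**Working it through.** The point turns on wording, and the plan gives no figure to reproduce. The check follows one event through the relevant sections.

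**Test case.** An AE begins after consent and before first dose at Grade 1. It continues under one record and reaches Grade 4 on treatment.

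1. *Is it collected?* Yes. Section 9.1.3 starts collection at consent.
2. *Is it a TEAE?* No. Its onset date is before the study drug start date, and Section 10.2.2.4 has no other route into the definition.
3. *Does the highest-grade rule bring it in?* No. That rule covers AEs that occur more than once. It selects a grade among occurrences and does not address a single continuing record, nor does it change which records are TEAEs.
4. *Does a recording rule bring it in?* Only partly. Section 9.1.3 says: "Clinically significant changes in physical examination findings and objective test findings should also be recorded as AEs". It also asks for abnormal test findings that lead to a dosage change, discontinuation, intervention or diagnostic work-up. Neither instruction covers a symptom such as fatigue, and neither says that a grade increase gets a new record with its own onset date. Two sites could enter the same course differently, one as a TEAE and one not.
5. *Is it visible elsewhere?* In the all-AE tabulation, yes. That tabulation pools screening-period and on-treatment events, so it cannot show that the rise in grade followed dosing. If the event is a laboratory value, the shift tables show it. They do not cover clinical events.

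**What one omission does to a table row.** A row (one term at one grade) changes only if the patient has no other qualifying record for it. Section 4.1 plans 21 to 42 patients in Part A. One omitted patient then lowers the pooled Part A incidence in that row by:

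- 1/42 = 2.4 percentage points with 42 patients
- 1/21 = 4.8 percentage points with 21 patients

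The effect within a single dose cohort is larger, but cohort sizes are not visible. These figures give the effect per patient, not an expected loss. The documents give no rate of pre-dose AEs that worsen, so the number of patients affected cannot be derived.

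**The case against.** The strongest reply is that little is hidden. Section 10.2.2.4 tabulates all AEs by grade, and Table 4 words the primary endpoint as AEs and SAEs. A reader might infer that worsening events disappear from the primary safety tables. The documents do not support that: the events leave the TEAE frequency tables, and the plan does not say which tables report the primary endpoint. This part of the reply stands. It also shows an ambiguity worth settling.

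A second reply concerns baseline conditions. Section 5.2 records these as medical history, and Section 9.1 ties an AE to a temporal association with use of the product. If a medical-history condition worsens on drug, the worsening may be entered as a new AE with an on-treatment onset, and it then meets the present definition. A reader might infer that every condition present at entry is lost. That does not follow. The clear gap is the AE that starts between consent and first dose and continues under one record.

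Third, other outputs catch some worsening. DLTs are tabulated and listed. QTcF, vital signs and weight are summarized as change from baseline, and ECOG status is summarized. Part A has separate primary endpoints for clinically significant ophthalmology and ECG changes. Exclusion criteria 5 and 6 (retinal disease, serious active infection) limit some candidate events at entry. All of this narrows the gap, but none of it puts the event into a TEAE table.

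Finally, Section 10.2.2.4 leaves full details to the SAP, and no separate SAP text, eCRF or data management plan is available here. A worsening rule may exist there. As it stands, however, the protocol fixes the definition without one.

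**Conclusion.** The definition is incomplete and should be extended. Followed as written, it omits from the TEAE frequency tables any AE with onset between consent and first dose that increases in grade on treatment under the same record. The direction is under-counting of on-treatment incidence and severity. A material downward bias in the primary safety result would be a stronger reading, and it is not shown: the endpoint is not restricted to TEAEs, the all-AE tabulation retains the event, and any percentage lost would rest on rates that the documents do not contain.

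The conclusion rests on two assumptions: that a grade increase is not routinely opened as a new record with its own onset date, and that no SAP or eCRF rule outside these documents already covers the case. If either is wrong, the remaining need is to state the rule in Section 10.2.2.4.

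**What to change.** - **Definition.** In Section 10.2.2.4 and the SAP, extend the TEAE definition to any AE with onset before the study drug start date whose NCI CTCAE grade increases on or after that date. Keep the same end of window (30 days after permanent discontinuation, or new anti-cancer therapy if earlier). State that the comparison is with the grade held immediately before first dose.
- **Recording.** In Section 9.1.3, state that worsening of a pre-existing medical-history condition is entered as an AE, with the date of worsening as its onset. For a continuing AE, capture the date of grade increase in the eCRF if it is not already captured.
- **Primary tables.** State whether the primary safety tables use all AEs or TEAEs.

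The cost is a sentence or two in each place, a small amount of extra data capture, possibly some queries to date grade changes for patients already entered, and slightly higher reported TEAE rates. Sample size, dosing and efficacy analyses are unaffected. Section 10.2.4 allows SAP updates before the Part D database lock, so the analysis wording can be changed within the existing process.
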